6.2 Secondary Efficacy Endpoints and Analyses

Clinically meaningful worsening of COVID-19 through Day 15

The analysis of the proportion of subjects who met the criteria of an increase of at least 2 points on the Ordinal Scale for Clinical Improvement through Day 15 within each treatment group will be performed using the method described above in Section 6.1.

Ordinal Scale for Clinical Improvement

Clinical improvement is defined as a reduction of at least 1 point on the Ordinal Scale. The time to the first occurrence of clinical improvement will be estimated using the KM method. The KM estimates along with 95% CI, and survival curves will be provided. Based on the KM estimates, the probabilities of experiencing clinical improvement and associated 95% CIs on Days 15 and 29 will be reported; in addition, the 25%, 50% (median), and 75% percentiles of the time to clinical improvement with associated 95% CIs will be provided, as data permit. The survival rates between treatment groups will be compared using Log-rank test. The p-value from Log-rank test will be presented.

In addition, the time to the first occurrence of resolution of COVID-19 defined as an Ordinal Scale of 0 will also be evaluated, using the KM method described above for the analysis of time to clinical improvement.

The progression of COVID-19 severity as measured by the Ordinal Scales through Day 29 will be evaluated by graphical illustrations using stacked bar chart for each treatment group. The X axis representing time points and Y axis representing the cumulative number of subjects for each Ordinal Scale. Each bar is divided into a number of sub-bars stacked end to end corresponding to different Ordinal Scales.

The changes in Ordinal Scales through Day 29 will be examined using box and whisker plots for each treatment group. The X axis representing the post-baseline time points and the Y axis representing the change from baseline in Ordinal Scales at each post-baseline visit.

The absolute value and change from baseline in the Ordinal scale from Day 1 through Day 29 will be summarized by treatment group and visit using descriptive statistics.

Symptom Score

The symptoms due to SARS-CoV-2 infection will be assessed and the symptom scores (Cough (0-3), Shortness of breath or difficulty breathing (0-3), Muscle aches or fatigue (0-3), Fever (0-4)) will be recorded in the eCRF.

The respiratory symptom score will be calculated by summing the symptom scores from Cough and Shortness of breath or difficulty breathing. The scores from each symptom together with calculated respiratory symptom scores will be summarized by presenting the number and percentage of subjects for each category by visit and treatment group.

The time to the first occurrence of resolution of symptoms defined as the time from the first symptom score of ≥ 1 to a symptom score of 0 will be estimated using the KM method. If a subject had a symptom score of 0 from Baseline through Day 29, then that subject will be excluded from the analysis.

Time to Resolution of Symptoms (days) = (Date of the first symptom score of 0 since the initial score of ≥ 1) - (Date of the initial symptom score of ≥ 1 at or after Baseline) + 1

For each individual symptom and the respiratory symptoms (cough, shortness of breath and difficulty breathing), the KM estimates along with 95% CI, and survival curves will be provided. Based on the KM estimates, the probabilities of experiencing the resolution and associated 95% CIs on Days 15 and 29 will be reported; in addition, the 25%, 50% (median), and 75% percentiles of the time to resolution with associated 95% CIs will be provided, as data permit. The survival rates between treatment groups will be compared using Log-rank test. The p-value from Log-rank test will be presented.

In addition, the time to the first occurrence of improvement of symptoms defined as the time from the initial symptom score of ≥ 1 to a reduction of ≥ 1 point on initial symptom score will also be evaluated for each individual symptom and the respiratory symptoms (cough, shortness of breath and difficulty breathing), using the KM method described above for the analysis of time to resolution of symptoms.

If a subject had a symptom score of 0 from Baseline through Day 29, then that subject will be excluded from the analysis.

Time to Improvement of Symptoms (days) = (Date of the first reduction of ≥ 1 point on initial symptom score of ≥ 1) - (Date of the initial symptom score of ≥ 1 at or after Baseline) + 1

A radar plot will be created by presenting each symptom score at each time point by treatment group.

SARS-CoV-2 Test

The SARS-CoV-2 tests will be performed at the end of the study or early discontinuation visit.

If the test result for a subject is missing at the end of the study or early discontinuation visit, then the subject will be excluded from the analysis. The proportion of subjects with positive test results within each treatment group will be presented along with a two-sided exact (Clopper-Pearson) 95% CI.

The observed difference in the proportion of subjects with positive test results between treatment groups along with the exact unconditional 95% CI for risk difference will be calculated. The null hypothesis of no difference in proportions of subjects with positive test results between treatment groups will be tested using Fisher's exact method and the p-value will be reported.

Mortality Rate through Day 29

Subject status (Alive/Death) will be recorded in the database. If the vital status of the subject is missing at the end of the study, then the subject will be excluded from the binomial analysis for the mortality rate. The subject will be included in the Kaplan-Meier (KM) analysis with right censoring at the date the subject was last known to be alive.

The mortality rate (proportion of subjects who die) through Day 29 within each treatment group will be analyzed and compared using the method as described in Section 6.1.

If deemed appropriate, an alternative analysis will be performed in which the survival rates will be estimated using the KM method. The KM estimates along with 95% CIs and survival curves will be provided. Based on the KM estimates, the survival probabilities and associated 95% CIs on Days 15 and 29 will be reported; in addition, the 25%, 50% (median), and 75% percentiles of the survival time with associated 95% CIs will be provided, as data permit. The survival rates between treatment groups will be compared using Logrank test and the p-value from Logrank test will be presented.

Subjects requiring ICU admission

Subject data pertaining to ICU admission will be recorded in the database.

The proportion of subjects who are admitted to the ICU from Day 1 to Day 29 within each treatment group will be presented along with a two-sided exact (Clopper-Pearson) 95% confidence interval (CI).

The observed difference in the proportion of subjects requiring ICU admission between treatment groups along with the exact unconditional 95% CI for risk difference will be calculated. The null hypothesis will be tested using Fisher's exact method and the p-value will be reported.

Subjects who have died without ICU admission during the study will be counted as requiring ICU admission for the analysis.

Number of ICU Days

The number of ICU days from Day 1 to Day 29 will be calculated based on the ICU admission and discharge dates recorded in the eCRF. The calculated number of ICU days will be compared between treatment groups using 2-sided Student's t-test. The 95% CI and p-value will be presented.

If the Student's t-test normality assumption is found to be clearly violated, a sensitivity analysis will be performed using a non-parametric Wilcoxon rank-sum test. The p-value from the test will be presented.

Subjects who died will be assigned as hospitalized in the ICU for the number of days remaining from the day of death to Day 29 for the analysis. Subjects who are alive and never admitted into the ICU will be included in the analysis with a value of zero ICU days.

Subjects who were at ICU at study completion will be assigned an ICU end date equal to the date of completion for the purpose of deriving number of ICU days.

Subjects requiring mechanical ventilation

Subject data pertaining to mechanical ventilation use will be recorded in the database.

The proportion of subjects who were on mechanical ventilation from Day 1 to Day 29 within each treatment group will be analyzed and compared using the method described above for the analysis of subjects requiring ICU admission.

Subjects who have died without mechanical ventilation during the study will be counted as requiring mechanical ventilation for the analysis.

Number of days on mechanical ventilation

The number of days on mechanical ventilation from Day 1 through Day 29 will be calculated based on the start/stop dates of mechanical ventilation recorded in the eCRF. Number of days on mechanical ventilation will be compared between treatment groups using 2-sided Student's t-test. The 95% CI and p-value will be presented.

If the Student's t-test normality assumption is found to be clearly violated, a sensitivity analysis will be performed using a non-parametric Wilcoxon rank-sum test. The p-value from the test will be presented.

Subjects who died will be assigned as being on mechanical ventilation for the number of days remaining to Day 29 for the analysis. Subjects who had mechanical ventilation ongoing at study completion will be assigned a mechanical ventilation end date equal to the date of completion for the purpose of deriving duration of mechanical ventilation. Subjects who are alive and never placed on mechanical ventilation will be included in the analysis with a value of zero days on mechanical ventilation.

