5. BACKGROUND

This protocol is being conducted under a COVID-19 specific IND filed with the Division of Pulmonary, Allergy and Critical Care of the FDA and is intended to provide preliminary data on the efficacy and safety of PUL-042 in subjects positive for SARS-CoV-2 infection. Evaluation of these data will determine the feasibility of advancing to Phase 3 clinical development to pursue an NDA filing and the potential for Emergency Use Authorization.

This section includes a brief summary of the rationale for clinical investigation of PUL-042 and a summary of the nonclinical data available on PUL-042. More detailed information can be found in the Investigator's Brochure.

[figure not shown]

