3.2 Treatment

3.2.1 Randomization Scheme and Treatment Arm Assignment

Subjects will be randomly assigned to receive PUL-042 Inhalation Solution or placebo in a 1:1 ratio. A central randomization system, the Medication Assignment Center (MAC; CTI Clinical Trial and Consulting Services), will be used for this study.

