4. GENERAL CONSIDERATIONS FOR DATA ANALYSIS

Unless otherwise specified, continuous variables will be summarized using descriptive statistics

(n, mean, standard deviation, median, minimum, and maximum). Categorical variables will be summarized showing the number and percentage of subjects within each category.

Summary results will be provided for each treatment group. All tabulations will be based on pooled data across centers.

Unscheduled visits will be excluded from the summaries but will be included in the data listings.

All statistical tests will be two-sided and tested at the 5% level of significance.

Analyses will be performed using SAS for Windows statistical software, version 9.4 or higher (SAS, Cary, NC), except where other software may be deemed more appropriate.

CTI will perform all efficacy and safety analyses described in this SAP.

Subject data will be listed, sorted by treatment group and subject number. When applicable, listings will be additionally sorted by visit and assessment date/time.

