4.5 Multiple Comparisons

Because of the exploratory nature of this study, there will be no adjustment for multiple comparisons.

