6.1 Primary Efficacy Endpoint and Analysis

The primary efficacy variable is the clinically meaningful worsening of COVID-19 within 28 days from the start of experimental therapy.

The Ordinal Scale for Clinical Improvement is a 9-point scale that measures disease severity. For this study, an increase of 2 or more points is considered meaningful worsening of disease ([Table 2](#)). This endpoint considers changes in disease severity that are observed at any time over the course of this study.

The Ordinal Scale for Clinical Improvement to be used in this study is derived from a draft scale proposed by the World Health Organization^[1] for clinical improvement as presented below:

Table 2 Ordinal Scale for Clinical Improvement (Derived from draft WHO scale)^[1]

Descriptor	Score
No clinical or virological evidence of infection	0
Infected but no limitation of activities	1
Limitation of activities	2
Hospitalized not requiring oxygen therapy (SpO ₂ > 93% on room air)	3
Oxygen by mask or nasal prongs	4
Non-invasive ventilation or high-flow oxygen	5
Intubation and mechanical ventilation	6
Ventilation + additional organ support- pressors, RRT, ECMO	7
Death	8

The null hypothesis is that there is no difference in proportions of subjects with clinically meaningful worsening of COVID-19 through Day 29 between randomized treatment groups; $H_0: \pi_t - \pi_c = 0$. The alternative hypothesis is that the proportions of subjects with clinically meaningful worsening of COVID-19 through Day 29 are different between the treatment groups; $H_1: \pi_t - \pi_c \neq 0$.

Subjects who had an increase of 2 or more points in Ordinal Scale from the baseline will be treated as meeting the criteria for clinically meaningful worsening of COVID-19. The proportion of subjects who met the criteria within each treatment group will be presented along with a two-sided exact (Clopper-Pearson) 95% confidence interval (CI).

The observed difference in the proportion of subjects meeting the criteria between treatment groups along with the exact unconditional 95% CI for risk difference will be calculated. The null hypothesis will be tested using Fisher's exact method and the p-value will be reported.

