9. SAMPLE SIZE AND POWER CALCULATIONS

The trial size of 100 subjects (50 PUL-042 inhalation solution: 50 placebo) was chosen based on clinical considerations. The rates of infection to adequately estimate a sample size for a statistically significant result are unknown.

Enrolled subjects will be randomized with equal probability to receive blinded treatment consisting of either PUL-042 or placebo.

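### The 12 recovery time-to-event analyses plan only a log-rank p-value between arms, with no effect estimate and interval; the five symptom-resolution tests could also use the Baseline score

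*SAP*

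**What the plan says.** SAP 6.2 defines time to improvement and time to resolution on the Ordinal Scale. It defines the same two outcomes for each of four symptoms and for the respiratory sum of cough and shortness of breath. Symptom resolution is "defined as the time from the first symptom score of ≥ 1 to a symptom score of 0". Symptom improvement is a drop of one point or more from the subject's own initial score. In both, the clock may start at Baseline or at a later visit.

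For each analysis the SAP plans curves, Day 15 and Day 29 probabilities and quartiles, with 95% CIs, by arm. Between arms it plans only this: "The survival rates between treatment groups will be compared using Log-rank test. The p-value from Log-rank test will be presented". It names no strata, covariate, hazard ratio or difference.

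For the primary endpoint (SAP 6.1), the observed difference "along with the exact unconditional 95% CI for risk difference will be calculated". SAP 6.2 applies the same approach to Day 15 worsening, viral positivity, mortality, ICU admission and ventilation. ICU and ventilator days get a t-test with a 95% CI.

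The setting is as follows:
- SAP 4: "All statistical tests will be two-sided and tested at the 5% level of significance".
- SAP 4.5: "there will be no adjustment for multiple comparisons".
- SAP 9: "The trial size of 100 subjects (50 PUL-042 inhalation solution: 50 placebo) was chosen based on clinical considerations". No power or effect size is given.
- Protocol 5: "Evaluation of these data will determine the feasibility of advancing to Phase 3 clinical development".

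**The concern.** The recovery endpoints are where a small trial in mostly non-ventilated patients may see most of its events, yet they are the only efficacy endpoints tested without a planned estimate of the treatment contrast. With about 50 per arm, many of the 12 p-values may be non-significant even if the drug works. Two separate per-arm intervals do not state the uncertainty of their difference, and that uncertainty is what a Phase 3 decision needs.

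There is also an efficiency question for symptom resolution. The test pools a subject starting at 1, who is one step from 0, with a subject starting at 3, who is three steps away. If the starting score predicts time to resolution, leaving it out dilutes the treatment comparison. The improvement endpoint is different, because each subject needs only a one-point drop from his or her own starting point.

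**Working it through.** The SAP states no power, event count or effect size for these analyses, so there is no planned figure to reproduce.

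**Count.** Ordinal Scale 2 (improvement, resolution). Symptom resolution 4 + 1 = 5. Symptom improvement 4 + 1 = 5. Total 2 + 5 + 5 = 12. The optional Kaplan-Meier analysis of mortality is not counted, because mortality already gets a risk difference.

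**Planned between-arm output, side by side**

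| Endpoint type | Estimate of contrast | 95% CI | p-value |
|---|---|---|---|
| Binary endpoints | risk difference | exact unconditional | Fisher |
| ICU and ventilator days | t-test comparison | yes | t-test |
| 12 recovery analyses | none | none | log-rank |

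**What a p-value alone hides (assumed values)**

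Difference in probability, 70% v 55%, 50 per arm, no censoring before Day 15:
- SE = sqrt(0.70×0.30/50 + 0.55×0.45/50) = sqrt(0.00420 + 0.00495) = 0.0957.
- 95% CI = 0.15 ± 1.96×0.0957 = -0.037 to 0.337.
- z = 0.15/0.0957 = 1.57, p about 0.12.

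Hazard ratio (HR) 1.3 with 80 events:
- SE(log HR) = 2/sqrt(80) = 0.224.
- 95% CI = exp(0.262 ± 1.96×0.224) = 0.84 to 2.02, p = 0.24.

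Both results are non-significant, and both leave a large benefit possible.

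**Starting score: simulation**

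Taken from the documents: two-sided 5% level, 1:1 allocation with no stratification factor named ("Subjects will be randomly assigned to receive PUL-042 Inhalation Solution or placebo in a 1:1 ratio"), and scores taken after Day 1 on Days 3, 6, 10, 15 and 29.

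Assumed, because the documents do not give them: 40 symptomatic subjects per arm, and starting scores 1/2/3 in 40/35/25%. There are two recovery models:
- Proportional hazards: daily rate = (ln 2/9) × HR × b^(score - 2), where b is the hazard ratio per starting point. A control subject starting at 2 then has a median of 9 days.
- One point at a time: each step has rate 2 × (ln 2/9) × rate ratio. Resolution needs as many steps as the starting score; improvement needs one.

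There were 2,000 trials per scenario, so the standard error of each figure is at most sqrt(0.25/2000) = 1.1 points. Both tests were run on the same simulated data.

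Power for resolution, unstratified → stratified by starting score:

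| Model | Effect 1.5 | Effect 1.8 |
|---|---|---|
| b = 1.0 (not prognostic) | 40% → 38% | 67% → 65% |
| b = 0.7 | 37% → 38% | 65% → 67% |
| b = 0.5 | 29% → 37% | 51% → 65% |
| b = 0.35 | 22% → 35% | 40% → 63% |
| One point at a time | 49% → 59% | 82% → 88% |

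With 25 per arm, the one-point model gave 33% → 37% and 59% → 67%. A separate repeat with 40 per arm gave 64% → 67% at b = 0.7 and a loss of about 3 points when the score was not prognostic.

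Power for improvement (one-point model): 39% → 37% and 71% → 69% with 40 per arm; 27% → 25% and 50% → 46% with 25 per arm.

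Respiratory sum (scores 1 to 6 assumed in 15/20/25/20/12/8%, 40 per arm):
- Six strata, resolution: 58% → 72% at rate ratio 1.5 in the one-point model, but 69% → 63% at HR 1.8 if the score is not prognostic.
- Two strata (1-2 v 3-6), resolution: 59% → 72% at rate ratio 1.5, with a loss of only 1 to 2 points if not prognostic.
- Six strata, improvement: 40% → 36%.

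Type I error was about 4% to 6% for both tests.

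**Unadjusted hazard ratio.** In a large-sample run in continuous time, a true HR of 1.8 appeared as about 1.75, 1.61 and 1.49 at b = 0.7, 0.5 and 0.35.

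**The case against.** The best defence is that the information is nearly all there. Per-arm Day 15 and Day 29 probabilities are reported with intervals, so the point difference is a subtraction and its standard error follows from the two Greenwood standard errors. SAP 6.3 allows additional analyses. These are secondary analyses that SAP 4.5 treats as exploratory, and the primary and other binary endpoints do carry effect estimates. This lowers the stakes but does not close the gap. The SAP does not say how the per-arm intervals are formed, it plans no contrast, and SAP 6.3 names no analysis that supplies one. An effect measure chosen after unblinding also carries less weight, and an exploratory aim favours estimation over testing.

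On stratification the defence is stronger. An unstratified log-rank test is a legitimate choice. The gain depends on prognostic strength that the documents do not give, and it becomes a small loss if the score does not matter. The initial score can also be recorded after dosing, so it is a poor stratifier; a pre-dose score is needed. A hazard ratio has its own difficulty, since five post-baseline visits produce heavily tied event times. All of this stands and shapes the fix.

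The Ordinal Scale analyses also mix starting scores (eligibility is 4 or less). Stratifying those was not examined, so nothing is claimed or asked for there.

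**Conclusion.** The missing contrast is established from the text for all 12 analyses and rests on no assumption. It should be corrected.

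The stratification point is narrower. With 40 symptomatic subjects per arm and assumed inputs, the five resolution tests gain about 6 to 23 points of power if the starting score is strongly prognostic (b of 0.5 or below, or one-point-at-a-time recovery) and about 2 to 3 at b = 0.7. They lose about 1 to 3 if it is not prognostic. With 25 per arm the one-point model gained 4 and 8. The simulations gave every subject a positive starting score and did not model the four-point fever scale separately, so a stratum for Baseline score 0 is untested.

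A reader might infer more than the documents support:
- That the size of benefit can never be known. Per-arm estimates are planned; what is missing is the contrast and its interval.
- That all ten symptom tests lose power. For the five improvement tests stratifying gained nothing and lost about 2 to 4 points.
- That the planned test is biased or invalid. Its type I error is near 5%.
- That the Phase 3 decision has no effect estimates. The primary and other binary endpoints provide them.

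**What to change.** In SAP 6.2:
1. For each of the 12 analyses, report the between-arm difference in Kaplan-Meier probability at Day 15 and Day 29 with a 95% CI, using SE = sqrt(SE_active² + SE_placebo²) from the Greenwood standard errors. Name a fallback for an arm in which everyone has recovered, where that standard error is zero.
2. Optionally add a hazard ratio with a 95% CI as supportive, stating the method for ties and whether it is adjusted.
3. For the five symptom-resolution analyses only, stratify the log-rank test by the pre-dose Baseline score of that symptom, as SAP 4.6 defines Baseline. Include a 0 stratum for subjects first symptomatic later, include score 4 for fever, and use grouped strata for the respiratory sum. Keep the unstratified test as supportive.
4. Leave the five symptom-improvement tests unstratified.

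The cost is SAP wording before unblinding and a few program statements. No new data or subjects are needed. The price of item 3 is a possible loss of 1 to 3 points of power if the Baseline score turns out not to be prognostic.

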7.2. Subject Selection

7.2.1. Inclusion Criteria

Subjects aged 18 years or older must fulfill all of the following inclusion criteria to be eligible for the study:

1. Subjects must have a positive test for SARS-CoV-2.
2. COVID-19 signs and symptoms such as (fever, cough, shortness of breath or fatigue) with onset within the 7 days prior to Screening and/or within 9 days of the first dose administered on Day 1
3. Subjects should be Ordinal Scale for Clinical Improvement score of 4 or less
4. Subjects receiving oxygen should have pulse oximetry $\geq 93\%$ on 3 liters per minute of oxygen or less delivered by nasal prongs
5. Subjects can be receiving standard of care (SOC) for COVID-19, this includes marketed therapies or therapies with Emergency Use Authorization (EUA) for COVID-19 treatment.
6. Subject's spirometry (FEV₁ and forced vital capacity [FVC]) must be $\geq 70\%$ of predicted value.

7. If female, the subject must be surgically sterile or \geq 1 year postmenopausal. If of child-bearing potential (including being $<$ 1 years postmenopausal) and, if participating in sexual activity that may lead to pregnancy, the subject agrees to use an effective dual method of birth control (acceptable methods include intrauterine device, spermicide, barrier, male partner surgical sterilization, and hormonal contraception) during the study and through 30 days after completion of the study.
8. If female, must not be pregnant, plan to become pregnant, or nurse a child during the study and through 30 days after completion of the study. A pregnancy test must be negative at the Screening Visit, prior to dosing on Day 1.
9. If male, must be surgically sterile or, if not surgically sterile and if participating in sexual activities that may lead to pregnancy, be willing to practice two effective methods of birth control (acceptable methods include barrier, spermicide, or female partner surgical sterilization) during the study and through 30 days after completion of the study.
10. Must have the ability to understand and give informed consent.

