7.11. Study Days 3, and 6 (Study Drug Administration)

All assessments should occur ± 1 day from the scheduled Study Day.

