7.15. Study End (Day 29)

Assessments should occur within +2 days of target Study Day.

Subjects should be followed to Day 29 (28 days post-initial dose of study drug).

- Women who can become pregnant will take a urine pregnancy test. If the test is positive, the results will be confirmed with a blood pregnancy test.
- Nasopharyngeal or oropharyngeal sample for SARS-CoV-2 testing
- SARS- CoV-2 infection symptom score
- Ordinal Scale for Clinical Improvement assessment
- Adverse event assessment
- Concomitant medication assessment

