2.2.2 Secondary Efficacy Endpoints

The secondary efficacy endpoints include the following:

- The difference in the proportion of patients with clinically meaningful worsening of COVID-19 within 14 days from the start of experimental therapy, as indicated by an increase of at least 2 points on the Ordinal Scale for Clinical Improvement.
- Ordinal Scale for Clinical Improvement during the study to determine time course of severity and resolution of disease
- SARS-Cov-2 Symptom Score during the study to determine the time course of disease symptoms and resolution of symptoms
- SARS-Cov-2 test result at Day 29
- All-cause mortality rate through Day 29
- Proportion of subjects requiring ICU admission from Day 1 to Day 29
- Number of ICU Days from Day 1 to Day 29
- Proportion of subjects requiring mechanical ventilation from Day 1 to Day 29
- Number of days on mechanical ventilation from Day 1 to Day 29

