4.4 Handling of Dropouts or Missing Data

Except for the time to event endpoints (Table 1), partial end dates of prior and concomitant medications (Section 5.6), and partial onset dates of AEs (Section 7.2.1), all other missing data

will be treated as missing and no method for imputation is planned.

Missing data on the time to event endpoints will have events coded as right censored per the following table:

Table 1 Missing Data Coding for Time to Event Data Analyses

Endpoint	Right Censoring
Time to clinical improvement on Ordinal Scale	Subject who did not meet the criteria for clinical improvement on Ordinal Scale or died at any time during follow-up will be right censored as of the date of last non-missing assessment of Ordinal Scale on or prior to Day 29.
Time to resolution of disease	Subject who did not meet the criteria for the resolution of disease or died at any time during follow-up will be right censored as of the date of last non-missing assessment of Ordinal Scale on or prior to Day 29.
Time to resolution of symptoms	Subject who did not meet the criteria for the resolution of symptoms or died at any time during follow-up will be right censored as of the date of last non-missing assessment of symptoms on or prior to Day 29.
Time to clinical improvement on symptoms	Subject who did not meet the criteria for clinical improvement on symptoms or died at any time during follow-up will be right censored as of the date of last non-missing assessment of symptoms on or prior to Day 29.
Subject Survival	Subjects who are still alive as of the last known follow-up will be right censored as of the date of last subject contact when the subject was known to be alive.

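### Symptom resolution and improvement: for subjects at 0 at Baseline, post-dose scores decide entry and time zero, so the log-rank test can reflect who entered instead of how fast symptoms cleared

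*SAP*

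**What the plan says.** SAP 6.2 (Symptom Score) analyses four symptoms and a respiratory sum score (cough plus shortness of breath) for time to resolution (score 0) and time to improvement (a fall of at least 1 point). Both use Kaplan-Meier curves and a log-rank p-value.

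- Entry: "If a subject had a symptom score of 0 from Baseline through Day 29, then that subject will be excluded from the analysis". Anyone with a positive score at any visit is included.
- Clock: the formula subtracts the date of the initial score of at least "1 at or after Baseline) + 1".
- Reporting: "the probabilities of experiencing the resolution and associated 95% CIs on Days 15 and 29 will be reported".
- Censoring (SAP 4.4, Table 1): subjects without the event are "right censored as of the date of last non-missing assessment of symptoms on or prior to Day 29".

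Baseline is the last value before first dose (SAP 4.6). Eligibility requires no particular symptom; Protocol 7.2.1 lists "COVID-19 signs and symptoms such as (fever, cough, shortness of breath or fatigue" as examples. A score of 0 on one item at Baseline is therefore allowed.

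**The concern.** For a subject at 0 at Baseline on an item, both membership of the analysis and time zero are set by what happens after dosing. If treatment changes how often new symptoms appear, the two arms contribute differently selected groups. If new episodes also clear at a different speed from those present at Baseline, the mix of fast and slow episodes differs by arm, and the log-rank test registers this as a difference in clearing speed. If PUL-042 prevents new symptoms and new episodes are short, that benefit counts against the drug.

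Using only part of the ITT set is not in itself the objection, since the fix does so too. The objection is selecting after dosing instead of before it.

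Nothing planned corrects this. The sensitivity analysis in SAP 6.3 concerns the primary endpoint. The by-visit score tables would show an onset imbalance but leave the p-value as it is. Five scores by two endpoints give ten such p-values.

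A second defect does not depend on the drug. For a late-onset subject, the Kaplan-Meier Days 15 and 29 count from the first positive score, not from first dose.

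**Working it through.** The documents give no rate, event count or power for these endpoints, so there is no figure to reproduce. The rule was checked by simulation and the labels by arithmetic.

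**Who enters.** With N = 50 per arm (SAP 9), Baseline prevalence p and onset rate q among Baseline-0 subjects, the expected number analysed per arm is 50p + 50(1 − p)q.

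- p = 50%, q = 10%: 25 + 2.5 = 27.5. With q = 30%: 25 + 7.5 = 32.5.
- p = 30%, q = 5%: 15 + 1.75 = 16.75. With q = 30%: 15 + 10.5 = 25.5.

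**Size of the bias (resolution only).** From the documents: 50 per arm, visits on Days 1, 3, 6, 10, 15 and 29, the SAP time formula, and a two-sided 5% test (2.5% per side). Assumed: baseline symptoms resolve exponentially with median 12 days in both arms, so PUL-042 has no effect on them; new onset occurs at Day 3, 6 or 10. New episodes are gone at the next visit, or last half as long as baseline ones (median 6 days), or as long. There were 20,000 trials per cell (Monte Carlo standard error about 0.11 points at 2.5%, 0.23 at 12%). Each entry is the percentage of trials with a false finding for the arm named.

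| Baseline prevalence | Onset, PUL-042 v placebo | Falsely better | One visit | Half as long | Same length |
|---|---|---|---|---|---|
| 30% | 20% v 10% | PUL-042 | 6.6 | 4.4 | 3.3 |
| 30% | 30% v 10% | PUL-042 | 12.7 | 6.3 | 3.5 |
| 30% | 5% v 30% | placebo | 19.3 | 8.7 | 3.7 |
| 50% | 10% v 10% | PUL-042 | 2.5 | 2.6 | 2.6 |
| 50% | 15% v 10% | PUL-042 | 3.7 | 3.1 | 2.9 |
| 50% | 20% v 10% | PUL-042 | 5.3 | 3.8 | 3.0 |
| 50% | 30% v 10% | PUL-042 | 8.7 | 5.0 | 3.5 |
| 50% | 5% v 30% | placebo | 11.7 | 6.1 | 3.6 |
| 70% | 20% v 10% | PUL-042 | 3.5 | 3.3 | 2.7 |
| 70% | 30% v 10% | PUL-042 | 5.6 | 3.8 | 3.0 |
| 70% | 5% v 30% | placebo | 6.5 | 4.5 | 3.2 |

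At 90% prevalence the maximum is 3.7%. New episodes twice as long as baseline ones reverse the direction, to at most 4.7%. At 50% prevalence, moving the baseline median between 6 and 20 days gives 7.4–10.2% for 30% v 10% onset with one-visit episodes, and 9.7–13.8% for 5% v 30%. Restricting to Baseline-symptomatic subjects gives 2.3–2.9% per side in all 80 cells run.

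**Second simulation, other assumptions.** Here mean clearance was 10 days for baseline episodes and 5, 10 or 20 days for new ones; onset was 40/40%, 20/60% or 10/70% (PUL-042/placebo); prevalence was 30% or 50%; 4,000 trials per scenario. Two-sided rejection, nominal 5%:

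- equal onset: 4.6–5.5%
- unequal onset, equal clearing: 5.6–6.8%
- both unequal: 6.2–10.7%
- Baseline-symptomatic subjects only: 4.8–5.8% in all 18 scenarios

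The small excess with equal clearing comes from the unequal visit gaps: an episode first seen on Day 15 can be seen resolved only on Day 29.

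**Day labels.** If the first positive score is on study Day a and the last visit on Day f, clock day 15 falls on study Day a + 14 and follow-up ends at clock day f − a + 1. The windows are: Days 3 and 6, "All assessments should occur ± 1 day from the scheduled Study Day"; Day 10 ±1 and Day 15 +1 (Protocol 7.12, 7.13); final visit, "Assessments should occur within +2 days of target Study Day".

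| First positive visit | Clock day 15 = study Day (on schedule; with windows) | Follow-up ends, clock day (on schedule; with windows) |
|---|---|---|
| Day 3 | 17; 16–18 | 27; 26–30 |
| Day 6 | 20; 19–21 | 24; 23–27 |
| Day 10 | 24; 23–25 | 20; 19–23 |
| Day 15 | 29; 29–30 | 15; 14–17 |

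f − a + 1 ≥ 29 holds only for (a, f) = (2, 30), (2, 31) and (3, 31): a Day 3 visit with a late final visit. The upper ends treat Day 29 in the censoring rule as the nominal visit. If it means the actual study day, f is at most 29 for an unresolved subject. The longest follow-up is then 29 − 2 + 1 = 28, so no unresolved late-onset subject reaches clock day 29.

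**The case against.** If PUL-042 has no effect on symptoms at all, whole symptom histories are exchangeable between arms. Entry and time zero are then exchangeable too, and the log-rank test is valid. Every inflated cell needs a real drug effect on onset, so the error is misattribution of that effect, not type I error under no effect. This stands, and the 10% v 10% row shows it. But the analysis is presented as a comparison of clearing speed, and a p-value driven by onset does not answer that question.

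Per-side figures also look larger than the two-sided ones, because the other tail shrinks. At 50% prevalence, two-sided rejection for one-visit / half-length / same-length episodes is 6.1 / 5.3 / 5.0% (20% v 10%), 9.2 / 7.0 / 5.0% (30% v 10%) and 11.2 / 7.2 / 5.4% (5% v 30%). The largest entries in the table need low prevalence, a sixfold onset difference and very short episodes. The documents support none of these. Scores are taken before dosing on dosing days (Protocol 7.10.1, 7.11.1), and FEV1 falls are described as brief and usually asymptomatic (Protocol 5.4, 7.10.2). The respiratory score is positive whenever either component is, so its Baseline prevalence is at least that of either item and the bias there is more limited.

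Finally, SAP 2.2.2 states the endpoint's purpose as "to determine the time course of disease symptoms and resolution of symptoms", and emerging symptoms belong to that course. The fix removes them from the log-rank comparison. That is a real cost, but the proposed onset comparison keeps them in the randomized analysis. The declared exploratory purpose (SAP 4.5) limits the consequences without making the p-value interpretable.

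**Conclusion.** The concern holds. SAP 6.2 makes entry and time zero depend on post-dose scores for anyone at 0 on an item at Baseline, and no planned analysis corrects the p-value. Material bias needs both an onset difference and a difference in clearing speed. Under moderate assumptions (50% prevalence, 20% v 10% onset) the inflated side is 3.8–5.3% when new episodes are shorter than baseline ones, against 2.5%. Under strong assumptions it reaches 12.7% in favour of PUL-042 or 19.3% against it. At high Baseline prevalence the effect is small. All rates are assumed, and the documents do not show that PUL-042 changes onset. Improvement has the same entry rule and time origin but was not simulated, so no size is claimed for it.

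The day-label defect applies to every late-onset subject whatever the drug does. The plan should be changed on both counts.

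**What to change.** In SAP 6.2, for each symptom and the respiratory score:

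- Make the Kaplan-Meier and log-rank analyses of resolution and improvement in ITT subjects with a Baseline score of 1 or more.
- Define time as the date of the first score of 0 (or first reduction of at least 1 point from Baseline) minus the date of first Study Drug administration, plus 1. Days 15 and 29 are then study days.
- For subjects at 0 at Baseline, report by arm the number and percentage with any later score of 1 or more through Day 29, with the risk difference and exact confidence interval as in SAP 6.1.
- The episode-duration curves may stay as a descriptive supplement, with the axis labelled as days since first positive score and no p-value.

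This changes SAP wording only and needs no new data. Resolution of newly emerging symptoms becomes descriptive, and each curve has fewer subjects: 25 instead of 27.5 per arm at 50% prevalence and 10% onset. For an assumed hazard ratio of 2 with 10% onset in both arms (10,000 trials per cell), power at 50% prevalence is about 60% with the fix. Under the current rule it is 63% if new episodes resolve like baseline ones and 55% if they last one visit. At 30% prevalence the corresponding comparisons, fix v current rule, are 40% v 46% and 38% v 32%.
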